#### **8.1.3 Safety Endpoints**

The safety endpoints for this study are:

- Incidence of ocular and non-ocular AEs
- Change in IOP
- Ocular signs (biomicroscopy)
- Change in VA
- Change in dilated fundus exam

#### 8.1.4 Tolerability Endpoints

The tolerability endpoints for this study are:

- Study drug sensation assessment at Visit 5 (Postoperative Day 8)
- Ocular symptoms at each follow-up visit

## 8.2 Hypotheses

The following multiple endpoints and multiple dose-vehicle comparison hypotheses will be tested using Bonferroni-based tree structured gatekeeping tests to control the overall type I error rate ( $\alpha = 0.05$ ) for the primary efficacy endpoints over the entire study. The hypotheses in Family 1 will be tested simultaneously. Each hypothesis in Family 2 will be eligible for rejection only if the corresponding hypothesis (TID, BID) in Family 1 is rejected.

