## 2.0 OBJECTIVE

The primary objective of this Phase 3 study is to evaluate the safety and efficacy of LE gel 0.38% (BID and TID) for the treatment of postoperative inflammation and pain following cataract surgery.

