### ***Family 1 of Hypotheses: Complete Resolution of AC Cells in the Study Eye at Visit 5***

$H_{011}$ : The difference, between subjects treated with LE gel 0.38% dosed TID and subjects treated with vehicle, in the proportion of subjects with complete resolution of AC cells in the study eye at Visit 5 (Postoperative Day 8) = 0.

$H_{A11}$ : The difference, between subjects treated with LE gel 0.38% dosed TID and subjects treated with vehicle, in the proportion of subjects with complete resolution of AC cells in the study eye at Visit 5 (Postoperative Day 8) does not equal 0, with superiority claimed if the difference favors LE gel 0.38% dosed TID.

$H_{012}$ : The difference, between subjects treated with LE gel 0.38% dosed BID and subjects treated with vehicle, in the proportion of subjects with complete resolution of AC cells in the study eye at Visit 5 (Postoperative Day 8) = 0.

$H_{A12}$ : The difference, between subjects treated with LE gel 0.38% dosed BID and subjects treated with vehicle, in the proportion of subjects with complete resolution of AC cells in the study eye at Visit 5 (Postoperative Day 8) does not equal 0, with superiority claimed if the difference favors LE gel 0.38% dosed BID.

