### 8.3 Sample Size

Approximately 588 subjects will be randomized in a 2:2:1:1 ratio to LE gel 0.38% dosed TID, LE gel 0.38% dosed BID, vehicle dosed TID, and vehicle dosed BID.

The 2 vehicle arms will be combined into 1 treatment group in the statistical analysis, and hence the study will have 3 treatment groups, ie, LE gel 0.38% dosed TID, LE gel 0.38% dosed BID, and (combined) vehicle group. Each of the three treatment groups will consist of approximately 196 subjects.

Estimates of efficacy used to calculate the sample size were based on the integrated database of 4 previous similar studies. Two of these studies were conducted with LE gel, 0.5% and vehicle, each dosed QID. One study was conducted with LE gel, 0.38%, dosed TID and BID. One study was conducted with LE gel, 0.38%, dosed BID.

Powers and sample sizes for individual comparisons were estimated using nQuery Advisor® 7.0 (Janet D. Elashoff, Copyright 1995-2007). Power to detect one or more differences and both differences was estimated by computer simulations of 250,000 trials.

#### 8.3.1 Complete Resolution of AC cells in the Study Eye at Visit 5

A two group  $\chi^2$  test with a 0.025 two-sided significance level will have 87% power to detect the difference between a LE gel 0.38% proportion,  $\pi_1$ , of 0.283 and a vehicle proportion,  $\pi_2$ , of 0.143 (odds ratio of 0.423) when the sample size in each group is 196. The two simultaneous  $\chi^2$  tests (TID and BID) will have 95% power to detect at least one of two such differences and 80% power to detect both differences.

#### 8.3.2 Complete Resolution of Pain in the Study Eye at Visit 5

Under the gatekeeping strategy, the power of each Family 2 (pain) hypothesis is limited by the power of the corresponding Family 1 (AC cells) hypothesis. However, the following statement shows that each Family 2 hypothesis is sufficiently powered in the event that the corresponding Family 1 hypothesis is rejected.

A two group  $\chi^2$  test with a 0.025 two-sided significance level will have 99% power to detect the difference between a LE gel 0.38% proportion,  $\pi_1$ , of 0.739 and a vehicle proportion,  $\pi_2$ , of 0.486 (odds ratio of 0.334) when the sample size in each group is 196.

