**Table 3: Bonferroni-based tree gatekeeping hypothesis structure**

Family	Null Hypothesis	Serial Rejection Set	Hypothesis Weight
F1	H 11 (TID AC Cells Resolution)	NA	1/2
	H 12 (BID AC Cells Resolution)	NA	1/2
F2	H 21 (TID Pain Resolution)	{ H 11 }	1/2
	H 22 (BID Pain Resolution)	{ H 12 }	1/2

95% confidence intervals will be constructed around the treatment differences using asymptotic normal approximations.

As a supportive analysis, these endpoints will be tested using the asymptotic Cochran Mantel-Haenszel statistic adjusting for site.

Supportive analyses of the primary analysis will be repeated on the per-protocol (PP) set.

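### Optional efficiency gain: the primary testing scheme is valid, but a regimen's 0.025 never passes to the other regimen's AC-cell test, so power for both AC-cell claims is about 80% where about 87% is available

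*Combined protocol and SAP*

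**What the plan says.** Section 8.2 places four primary hypotheses under an overall type I error of 0.05. Family 1 is AC-cell resolution at Visit 5, TID and BID each against pooled vehicle. Family 2 is Grade 0 pain at Visit 5, with the same two comparisons. On Family 1: "The hypotheses in Family 1 will be tested simultaneously". On the gate: "Each hypothesis in Family 2 will be eligible for rejection only if the corresponding hypothesis (TID, BID) in Family 1 is rejected".

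Table 3, titled "Bonferroni-based tree gatekeeping hypothesis structure", gives each AC-cell hypothesis weight 1/2 and shows NA for its serial rejection set. Each pain hypothesis also has weight 1/2 and depends only on its own regimen's AC-cell hypothesis. Nothing leads from Family 2 back to Family 1, or from one AC-cell hypothesis to the other.

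Section 8.3.1 sizes each AC-cell test at two-sided 0.025 with 196 per group. It gives 87% power for each comparison and says the pair "will have 95% power to detect at least one of two such differences and 80% power to detect both differences". Section 8.3 adds: "Power to detect one or more differences and both differences was estimated by computer simulations of 250,000 trials". Section 8.3.2 notes that "the power of each Family 2 (pain) hypothesis is limited by the power of the corresponding Family 1 (AC cells) hypothesis".

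Each regimen has its own claim. For BID on AC cells the alternative reads "with superiority claimed if the difference favors LE gel 0.38% dosed BID", and TID has the matching statement. Section 2.0 names both regimens in the objective. No section makes winning with both a condition of success.

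**The concern.** Suppose TID is rejected on AC cells and then on pain. Its branch is finished, and its 0.025 has no further use under Table 3. If the BID AC-cell p-value is 0.03, BID still fails on AC cells, and its pain hypothesis cannot be tested at all. A procedure with the same pain gates and the same 0.05 limit would reject BID AC cells and then test BID pain.

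The point therefore affects only a second regimen whose AC-cell p-value lies between 0.025 and 0.05 after the first has won on both endpoints. What is at stake is the power to claim both regimens, not the validity of the trial.

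**Working it through.** **Inputs (Sections 8.3.1 and 8.3.2).** AC-cell resolution 0.283 on LE gel (used for both regimens) and 0.143 on vehicle. Grade 0 pain 0.739 and 0.486. 196 per group, with one shared vehicle group. Pearson chi-squared tests.

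**1. The plan's figures reproduce.** For one AC-cell test at two-sided 0.025, the pooled rate is 0.213:

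power = Φ{[0.14·√196 − 2.2414·√(2·0.213·0.787)] / √(0.283·0.717 + 0.143·0.857)} = Φ{(1.960 − 1.298)/0.5705} = Φ(1.161) = 87.7%.

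Exact binomial enumeration gives 88.1%; the plan states 87%. For pain, the same formula gives 99.9%, against 99% stated.

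For joint power, let A(y) and B(y) be the chance that one regimen rejects in favour of LE at 0.025 and at 0.05, given y vehicle responders. Averaging over y by exact enumeration:

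- both at fixed 0.025, E[A²] = 80.2% (plan: 80%);
- at least one, E[1 − (1 − A)²] = 95.9% (plan: 95%).

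**2. No alpha passes within Family 1.** The algorithm is cited, not printed, but the stated 80% identifies it. If the second AC-cell test could use 0.05 once the first had passed at 0.025, the figure would be E[B² − (B − A)²] = 87.3%. Only fixed 0.025 tests give 80%.

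**3. Passing through the same regimen's pain test.** Take a Bonferroni graph with weight 1/2 on each AC-cell hypothesis and 0 on each pain hypothesis. The transitions are AC cells → own pain → other regimen's AC cells, each with weight 1. Because pain power at 0.025 is 99.9%, almost nothing is lost on the way. Results from 1,000,000 simulated trials:

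| Power at plan rates | Table 3 | Graph |
|---|---|---|
| Both AC-cell claims | 80.2% | 87.2% |
| At least one AC-cell claim | 96.0% | 96.0% |
| Each AC-cell claim | 88.1% | 91.6% |
| All four claims | 80.0% (80.1% if Family 2 weights are rescaled) | 87.2% |

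Whether Table 3 rescales weights within Family 2 depends on the cited references; no AC-cell figure is affected. A separate simulation put the graph's power for both at 87.3% to 87.4% for AC-pain latent correlations of 0, 0.3, 0.6 and 0.9. In no simulated trial did Table 3 reject a hypothesis that the graph did not, under either reading of Family 2.

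**4. Equivalent sample size.** Table 3 gives 87.1% for both AC-cell claims at 226 per group and 87.3% at 227. At 227 the total is 3 × 227 = 681, and 681 − 588 = 93.

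**5. Sensitivity.** The rates below are assumptions, not figures from the documents. Anything not listed stays at the plan's value.

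| Assumed LE rates | Gain for both AC-cell claims (points) |
|---|---|
| Plan rates | 7.1 |
| Pain 65% / 60% / 55%, both regimens | 6.0 / 3.5 / 1.1 |
| AC cells 32% / 25%, both regimens | 2.1 / 10.9 |
| BID only: AC cells 25%, pain 70% | about 10 |

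**6. Price in type I error.** All 15 null configurations were simulated (1,000,000 runs each, endpoint correlation 0 and 0.4, very large non-null effects). The highest familywise error was 0.0497 for Table 3 without rescaling and 0.0505 for the graph. The simulation standard error is √(0.05·0.95/1,000,000) = 0.0002, and a Bonferroni graph controls 0.05 by construction.

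The error rises from about 0.025 to 0.05 in four configurations: those where one regimen's AC-cell null is true, with or without its pain null, and everything else is effective. It rises in two more, a single true pain null, if Table 3 does not rescale within Family 2. With BID null on both endpoints and TID at plan rates, the chance of a false BID AC-cell claim favouring LE goes from 1.28% to 2.48%.

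**The case against.** The scheme is pre-specified, valid and fully disclosed. The sponsor simulated 95% for at least one and 80% for both, and accepted them. Section 1.0 asks whether BID and/or TID dosing may be effective, and at-least-one power, which fits that question best, gains nothing. The 93-subject equivalent prices a target the plan never set. All of this stands, and it is why the change is optional.

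The graph also adds a dependence the plan does not have. A BID AC-cell p-value of 0.04 would succeed or fail according to TID subjects' reported pain, whereas now Family 1 decisions never depend on Family 2. A sponsor may prefer each regimen's AC-cell result to stand alone, particularly as the chance of a false BID claim nearly doubles within the 0.05 limit. That is a real trade-off.

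The gain is conditional as well. It shrinks if pain power falls or if the AC-cell effect is large. Unequal regimens do not weaken the case: the gain was larger in the unequal scenario above.

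None of this disputes the arithmetic or the claim that the graph keeps every rejection Table 3 makes.

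**Conclusion.** The point holds as an optional improvement, not a defect. At the plan's rates, with both regimens equally effective, passing the freed 0.025 raises power for both AC-cell claims by about 7 points, from 80.2% to about 87%. That 87% is a joint power and should not be confused with the 87% in Section 8.3.1 for a single comparison. Power for at least one claim does not change.

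Across the assumed rates tried, the gain ran from 1.1 to 10.9 points. It cannot be negative, because the graph keeps every rejection that Table 3 makes. In exchange, the familywise error reaches the permitted 0.05 in configurations where about half is now unused, and one regimen's pain result can affect the other's AC-cell threshold.

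**What to change.** Before unmasking, replace Table 3 with this Bonferroni graph:

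- **Initial weights:** H11 1/2, H12 1/2, H21 0, H22 0.
- **Transitions, each with weight 1:** H11 → H21, H21 → H12, H12 → H22, H22 → H11.

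Suggested text: *Each AC-cell hypothesis is tested at 0.025. If it is rejected, the pain hypothesis of the same regimen is tested at 0.025. If one regimen rejects both, the other regimen's AC-cell hypothesis, and then its pain hypothesis, is tested at 0.05. The adjusted p-value of a hypothesis is the smallest overall level at which the graph rejects it.* The last sentence keeps the existing decision rule, which compares adjusted p-values with 0.05.

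The route through pain matters. Passing all the alpha directly between the two AC-cell tests would leave pain untested until both were rejected.

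Amend Section 8.2, Section 8.5.1.1 with Table 3, and the synopsis text on hypotheses and primary analysis. Update references 32 and 33, which support the tree procedure. In Section 8.3.1 and the synopsis sample-size text, restate the power for both AC-cell differences as about 87% at the assumed pain rates. Leave the at-least-one power and the per-test power at 0.025 as they are.

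**Cost:** a protocol and SAP amendment, with IRB approval before implementation (Section 9.6) at up to about 60 sites, and a few lines of code. No added subjects, visits or data. If another amendment is planned, the change could go with it.

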### ***Family 1 of Hypotheses: Complete Resolution of AC Cells in the Study Eye at Visit 5***

$H_{011}$ : The difference, between subjects treated with LE gel 0.38% dosed TID and subjects treated with vehicle, in the proportion of subjects with complete resolution of AC cells in the study eye at Visit 5 (Postoperative Day 8) = 0.

$H_{A11}$ : The difference, between subjects treated with LE gel 0.38% dosed TID and subjects treated with vehicle, in the proportion of subjects with complete resolution of AC cells in the study eye at Visit 5 (Postoperative Day 8) does not equal 0, with superiority claimed if the difference favors LE gel 0.38% dosed TID.

$H_{012}$ : The difference, between subjects treated with LE gel 0.38% dosed BID and subjects treated with vehicle, in the proportion of subjects with complete resolution of AC cells in the study eye at Visit 5 (Postoperative Day 8) = 0.

$H_{A12}$ : The difference, between subjects treated with LE gel 0.38% dosed BID and subjects treated with vehicle, in the proportion of subjects with complete resolution of AC cells in the study eye at Visit 5 (Postoperative Day 8) does not equal 0, with superiority claimed if the difference favors LE gel 0.38% dosed BID.

### ***Family 2 of Hypotheses: Complete Resolution of Pain in the Study Eye at Visit 5***

$H_{021}$ : The difference, between subjects treated with LE gel 0.38% dosed TID and subjects treated with vehicle, in the proportion of subjects with Grade 0 pain in the study eye at Visit 5 (Postoperative Day 8) = 0.

$H_{A21}$ : The difference, between subjects treated with LE gel 0.38% dosed TID and subjects treated with vehicle, in the proportion of subjects with Grade 0 pa in in the study eye at Visit 5 (Postoperative Day 8) does not equal 0, with superiority claimed if the difference favors LE gel 0.38% dosed TID.

$H_{022}$ : The difference, between subjects treated with LE gel 0.38% dosed BID and subjects treated with vehicle, in the proportion of subjects with Grade 0 pa in in the study eye at Visit 5 (Postoperative Day 8) = 0.

$H_{A22}$ : The difference, between subjects treated with LE gel 0.38% dosed BID and subjects treated with vehicle, in the proportion of subjects with Grade 0 pain in the study eye at Visit 5 (Postoperative Day 8) does not equal 0, with superiority claimed if the difference favors LE gel 0.38% dosed BID.

### 8.3 Sample Size

Approximately 588 subjects will be randomized in a 2:2:1:1 ratio to LE gel 0.38% dosed TID, LE gel 0.38% dosed BID, vehicle dosed TID, and vehicle dosed BID.

The 2 vehicle arms will be combined into 1 treatment group in the statistical analysis, and hence the study will have 3 treatment groups, ie, LE gel 0.38% dosed TID, LE gel 0.38% dosed BID, and (combined) vehicle group. Each of the three treatment groups will consist of approximately 196 subjects.

Estimates of efficacy used to calculate the sample size were based on the integrated database of 4 previous similar studies. Two of these studies were conducted with LE gel, 0.5% and vehicle, each dosed QID. One study was conducted with LE gel, 0.38%, dosed TID and BID. One study was conducted with LE gel, 0.38%, dosed BID.

Powers and sample sizes for individual comparisons were estimated using nQuery Advisor® 7.0 (Janet D. Elashoff, Copyright 1995-2007). Power to detect one or more differences and both differences was estimated by computer simulations of 250,000 trials.

#### 8.3.1 Complete Resolution of AC cells in the Study Eye at Visit 5

A two group  $\chi^2$  test with a 0.025 two-sided significance level will have 87% power to detect the difference between a LE gel 0.38% proportion,  $\pi_1$ , of 0.283 and a vehicle proportion,  $\pi_2$ , of 0.143 (odds ratio of 0.423) when the sample size in each group is 196. The two simultaneous  $\chi^2$  tests (TID and BID) will have 95% power to detect at least one of two such differences and 80% power to detect both differences.

#### 8.3.2 Complete Resolution of Pain in the Study Eye at Visit 5

Under the gatekeeping strategy, the power of each Family 2 (pain) hypothesis is limited by the power of the corresponding Family 1 (AC cells) hypothesis. However, the following statement shows that each Family 2 hypothesis is sufficiently powered in the event that the corresponding Family 1 hypothesis is rejected.

A two group  $\chi^2$  test with a 0.025 two-sided significance level will have 99% power to detect the difference between a LE gel 0.38% proportion,  $\pi_1$ , of 0.739 and a vehicle proportion,  $\pi_2$ , of 0.486 (odds ratio of 0.334) when the sample size in each group is 196.

## 8.4 Study Populations

**Intent to Treat (ITT):** The ITT population will include all randomized subjects. Analysis on the ITT sample will be used as the primary efficacy analysis and will be performed for all efficacy endpoints. Subjects will be analyzed in the treatment group to which they were assigned.

**Per Protocol (PP):** The PP population will include all ITT subjects who remain in study through Visit 5 (Postoperative Day 8) and who have not deviated from the protocol in any way likely to seriously affect the primary outcome of the study. Important protocol deviations related to study inclusion or exclusion criteria, conduct of the trial, subject management, or subject assessment will be identified prior to locking the study database.

Analyses on the PP sample will be used as a supplement to the ITT analyses and will be performed for the primary efficacy endpoints. Subjects will be analyzed in the treatment group to which they were assigned.

**Safety:** The safety population will include all subjects who received at least 1 dose of study drug. All randomized subjects will be assumed to have taken study drug unless otherwise confirmed. If it is confirmed that a subject never took a dose of study drug, then the subject will be excluded from all safety analyses. All subjects in the safety population will be analyzed according to the treatment they actually received and not according to the treatment they were assigned to receive, in the event of discrepancy.

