### 6.2.3 Subject Discontinuation

A subject MAY be discontinued (at the discretion of the Investigator, the Sponsor and/or the IRB/EC) prior to the final study visit for several reasons, including, but not limited to:

- A serious adverse event (SAE) occurring during the course of the study, which precludes continued treatment or follow-up
- The subject not following required study procedures
- If a subject exhibits intolerable adverse events (AEs, related or not related to the study treatment), or if a subject fails to show improvement in inflammation or the clinical status of inflammation worsens, the treating Investigator may opt to withdraw the subject from the trial and implement necessary intervention (ie, rescue therapy)

A subject MUST be discontinued prior to the final study visit for any of the following reasons:

- Voluntary withdrawal
- Death
- Pregnancy
- Rescue Medication
- Investigator decision that it is not in the best medical interests of the subject to continue participation in the investigation

Prior to discontinuing a subject, every effort should be made to contact the subject, schedule a final study visit (see Appendix A, Early Discontinuation visit), obtain as much follow-up data as possible, and to retrieve all study materials. Adverse events will be followed as described in [Sections 7.3](#) and [7.4](#). An early termination visit should take place within 7 days following the subject being discontinued. If a subject is discontinued during a given scheduled visit, the early termination procedures as outlined in Appendix A may be performed at that visit. Subject withdrawals will be documented clearly on the source document and applicable electronic case report form (eCRF).

Notification of subject discontinuations will be made to the Sponsor. Any subject discontinued from the study will not be replaced.

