#### 6.2.3.1     Rescue Medication

Subjects will be assessed at Visits 4 through 7 (Postoperative Days 3, 8, 15, and 18) for treatment rescue. Subjects with worsening or no change in the grade of inflammation in the study eye compared with the previous visit are eligible and may be considered for rescue medication. For subjects who meet either of these criteria, it is at the discretion of the Investigator when to begin rescue medication. The choice of rescue medication and dosing shall also be determined by the Investigator. Subjects requiring rescue medication for inflammation will stop treatment with the study drug and will be promptly discontinued from the study. The inflammation will not be reported as an adverse event (AE). The rescue medication will be recorded on the Concomitant Medication electronic case report form (eCRF) and the exit reason will be entered as “rescue medication” in the eCRF. Subjects who receive rescue medication will be counted as treatment failures as of the date of receiving rescue medication. Subjects who require rescue medication should return within 7 days following the date that rescue medication begins in order to undergo the procedures for the early termination visit.

NOTE: Rescue med that is required at V7 will not be recorded on the ConMed eCRF

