### 6.3.2 Disallowed Therapy

A disallowed medication may be administered in an emergency if the subject's safety is in jeopardy. If possible, the Medical Monitor should be consulted prior to administration of the disallowed medication (if not feasible, then as soon as possible afterwards) to determine whether the subject may continue in the study.

If a subject has taken any disallowed medication for any reason other than rescue therapy, record this as a protocol deviation and immediately contact Bausch + Lomb.

Disallowed medications include, but are not limited to the following:

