using the study drug and be withdrawn from study participation. Subjects requiring rescue medication will be considered treatment failures.

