#### **8.1.2 Secondary Efficacy Endpoints**

The secondary efficacy endpoints for this study include:

- Proportion of subjects with complete resolution of AC cells in the study eye at each visit and for each subject's final on-treatment visit
- Proportion of subjects with Grade 0 pain in the study eye at each visit and for each subject's final on-treatment visit
- Proportion of subjects with complete resolution of AC flare in the study eye at each visit and for each subject's final on-treatment visit
- Proportion of subjects with complete resolution of AC cells and flare in the study eye at each visit and for each subject's final on-treatment visit
- Change from baseline in AC cells and flare, combined and separately, at each follow-up visit
- Proportion of treatment failures at Visit 5 (Postoperative Day 8)

Other secondary or exploratory efficacy analyses may also be carried out as described in the study Statistical Analysis Plan.

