#### 8.5.1.1 Efficacy Endpoint Analyses

##### Analysis of Primary Efficacy Endpoints

The primary efficacy endpoints are the proportion of subjects with complete resolution of AC cells at Visit 5 (Postoperative Day 8) and the proportion of subjects with Grade 0 pain at Visit 5 (Postoperative Day 8). Primary efficacy analyses will be based on the intent-to-treat (ITT)

population with missing data imputed as failures (subjects placed on rescue medication prior to the visit being summarized will also be considered failures).

The primary efficacy analyses of the difference between each active treatment group and the combined vehicle treatment group at (Visit 5) Postoperative Day 8 will be tested using Pearson Chi-squared tests with p-values adjusted using a Bonferroni-based tree gatekeeping strategy with the structure shown in Table 3. Null hypotheses with adjusted p-values  $\leq 0.05$  will be rejected.

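### The per-protocol set drops every subject rescued before Visit 5, even one with no protocol deviation, so the supportive analysis of both primary endpoints is selected on an efficacy outcome

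*Combined protocol and SAP*

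**What the plan says.** **PP membership (Section 8.4).** There are two joint conditions. The first is retention: "The PP population will include all ITT subjects who remain in study through Visit 5 (Postoperative Day 8"). The second is the absence of any deviation serious enough to bear on the primary outcome. PP supplements ITT for the primary endpoints, and Section 8.5.1.1 (below Table 3) repeats the primary analysis on it.

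**Rescue.** Section 6.2.3.1 makes a subject eligible when the inflammation grade in the study eye has worsened or stayed the same since the preceding visit. The consequence is stated there: "Subjects requiring rescue medication for inflammation will stop treatment with the study drug and will be promptly discontinued from the study". Section 6.2.3 lists rescue medication under "A subject MUST be discontinued prior to the final study visit for any of the following reasons".

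**Rescue is not a deviation (Section 6.3.2).** "If a subject has taken any disallowed medication for any reason other than rescue therapy, record this as a protocol deviation".

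**Rescue is a failure.** Section 6.2.3.1: "Subjects who receive rescue medication will be counted as treatment failures as of the date of receiving rescue medication". Section 6.3.2, after Table 2: "Subjects requiring rescue medication will be considered treatment failures". For the ITT primary analysis, Section 8.5.1.1 adds that "subjects placed on rescue medication prior to the visit being summarized will also be considered failures", and Section 8.5.9 scores everyone who leaves before Visit 5 as a failure.

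**The concern.** A per-protocol analysis is read as showing what happens when subjects who departed from the protocol are set aside. Here it also sets aside subjects who followed the protocol exactly and whose treatment failed by the protocol's own definition. Membership depends on a post-randomization efficacy result, and the result may differ between active and vehicle.

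Two things follow. First, neither agreement nor disagreement between PP and ITT can be read cleanly, because removing deviators and removing failures are confounded. Second, the repeated primary analysis carries a rule that scores early rescue as failure, but if sites discontinue rescued subjects as required, nobody in PP is left for it to apply to.

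The planned outputs allow only a partial reconstruction. Section 8.1.2 lists "Proportion of treatment failures at Visit 5 (Postoperative Day 8") as a secondary endpoint, but Section 8.5.9 puts missing data and all early leavers into the failure category too. The rescue-therapy table in Section 8.5.4 has no time limit, and the disposition table in Section 8.5.5 counts discontinuation at any time. None is specified to give, by group, the number rescued before Visit 5 with no other reason for exclusion from PP. That number is what a reader would need in order to restore the PP denominator.

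**Working it through.** **1. The plan's own figures (Section 8.3).** Inputs: n = 196 per group, two-sided α = 0.025 (z = 2.2414), AC cell resolution 0.283 (LE gel) and 0.143 (vehicle), Grade 0 pain 0.739 and 0.486.

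Power = Φ{[√n·(p1 − p0) − z·√(2p̄(1 − p̄))] / √(p1(1 − p1) + p0(1 − p0))}

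- AC cells: p̄ = 0.213; (1.960 − 2.2414 × 0.5790)/0.5705 = 1.161, power 0.877 (stated 87%).
- Pain: p̄ = 0.6125; (3.542 − 2.2414 × 0.6890)/0.6653 = 3.00, power 0.999 (stated 99%).
- Simulation of 250,000 trials with a shared vehicle group: at least one AC difference 0.959 (stated 95%), both 0.803 (stated 80%).

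The stated power is not in dispute. These rates serve only as the base for what follows.

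**2. Who is dropped.**
- Rescue before Visit 5 leads to mandatory discontinuation (6.2.3, 6.2.3.1), so the retention condition fails and the subject is outside PP (8.4).
- Rescue is not a deviation (6.3.2), so this holds for fully compliant subjects.
- In ITT the same subject stays and is a failure (8.5.1.1, 8.5.9).
- No section returns the subject to PP.
- A subject first rescued at Visit 5 has stayed through Visit 5 and is not dropped by this rule.

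**3. Effect on the difference.** Let r1 and r0 be the shares rescued before Visit 5 on LE gel and vehicle. If all rescued subjects are ITT failures and rescue is the only PP exclusion, then

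PP rate = ITT rate / (1 − r)

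PP difference − ITT difference = p1·r1/(1 − r1) − p0·r0/(1 − r0)

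The difference shrinks only if [r0/(1 − r0)] / [r1/(1 − r1)] > p1/p0:
- AC cells: 0.283/0.143 = 1.98
- Pain: 0.739/0.486 = 1.52

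Break-even vehicle rescue (AC cells, pain) is 3.9% and 3.0% when LE rescue is 2%, and 9.4% and 7.4% when LE rescue is 5%.

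**4. Yardstick.** ITT 95% CI half-width = 1.96·√[p1(1 − p1)/196 + p0(1 − p0)/196]:
- AC cells: 1.96·√(0.3255/196) = 8.0 points
- Pain: 1.96·√(0.4427/196) = 9.3 points

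**5. Grid.** All rescue rates are assumptions. ITT differences are 14.0 (AC cells) and 25.3 (pain).

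| Rescue LE/vehicle | Removed per 196 (LE, vehicle) | Rescue odds ratio | PP difference, AC (shift) | PP difference, pain (shift) |
|---|---|---|---|---|
| 2%/2% | 4, 4 | 1.00 | 14.3 (+0.3) | 25.8 (+0.5) |
| 2%/5% | 4, 10 | 2.58 | 13.8 (−0.2) | 24.3 (−1.0) |
| 5%/5% | 10, 10 | 1.00 | 14.7 (+0.7) | 26.6 (+1.3) |
| 5%/8% | 10, 16 | 1.65 | 14.2 (+0.2) | 25.0 (−0.3) |
| 5%/10% | 10, 20 | 2.11 | 13.9 (−0.1) | 23.8 (−1.5) |
| 10%/10% | 20, 20 | 1.00 | 15.6 (+1.6) | 28.1 (+2.8) |
| 5%/15% | 10, 29 | 3.35 | 13.0 (−1.0) | 20.6 (−4.7) |
| 5%/20% | 10, 39 | 4.75 | 11.9 (−2.1) | 17.0 (−8.3) |
| 20%/20% | 39, 39 | 1.00 | 17.5 (+3.5) | 31.6 (+6.3) |

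Example, 5%/20%, pain: 0.739/0.95 − 0.486/0.80 = 0.778 − 0.6075 = 0.170.

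**The case against.** **PP is only supportive.** No hypothesis test, gatekeeping step or claim depends on it, and ITT handles rescue properly. This stands. It limits the importance of the point but does not remove it: an analysis planned as the supplement to both primary endpoints should isolate what it appears to isolate.

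**The effect is probably small.** Visit 4 is the only scheduled rescue assessment before Visit 5, rescue is discretionary even for eligible subjects, and shifts at low rates are well inside the CI half-widths. This also stands. Larger shifts need a strong imbalance or more rescue overall, and nothing in the documents shows either.

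**Completers answer a different question.** A subject rescued at Visit 4 has had only about two days of study drug, so a retained-to-Visit-5 set describes those followed on regimen, and Section 8.5.1.1 attaches the rescue-as-failure rule to ITT. The distinction is fair for most early leavers, whose Visit 5 outcome is unknown. It is weaker for rescued subjects, who already have a protocol-defined failure.

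**For pain the selection is indirect.** Rescue depends on inflammation, and a rescued subject may have no pain; the pain failure is assigned by rule. This is correct, and the pain column shows the removal of assigned failures. The selection is still on an efficacy outcome.

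**Existing tables nearly cover it.** They do so in part. The count by group of subjects rescued before Visit 5 with no other exclusion is not specified.

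**Conclusion.** The concern holds. As written, PP excludes every subject discontinued for rescue before Visit 5 whether or not that subject deviated, so the set is partly defined by treatment failure. The reading of the text is firm; the size is not.

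With rescue between 2%/2% and 5%/10% the PP difference moves by at most 1.5 points, in either direction. It can lose 2.1 (AC cells) and 8.3 points (pain) at 5%/20%, or gain 1.6 and 2.8 at 10%/10%. These figures rest on three assumptions: the rescue rates themselves, that the Section 8.3 planning rates already count rescues as failures (the section does not say), and that rescue is the only reason for leaving PP.

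This is worth correcting because the correction is cheap. It does not threaten the trial's primary conclusion.

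**What to change.** Add one exception to Section 8.4: a subject discontinued for rescue medication before Visit 5 who has no other deviation that would exclude that subject stays in PP and is scored as a failure on both primary endpoints. Keep the retention condition for all other early leavers, and report how many it removes by treatment group and reason. Settle this before unmasking.

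The cost is one clause and the matching derivation. Section 6.2.3.1 already records the rescue exit reason and the rescue medication, so no new data are needed, and neither care nor the rescue rules change. If rescue is the only source of early exclusion, the planned differences of 14.0 and 25.3 points are preserved in PP. The small price is that PP will then hold some subjects without an on-treatment Visit 5 assessment. Defining PP by deviations alone would also remove the problem, but it is a wider change: it would bring in early leavers whose Visit 5 outcome is simply missing.
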